7.9 Supportive Care Guidelines

a. Infection Prophylaxis

1. Extremely careful hand washing by all members of health care team is required.
2. Diet should exclude raw fruits, vegetables and unprocessed foods.
3. Antibiotic prophylaxis with oral antimicrobial agents is strongly recommended for all patients as indicated in the following table.

AGENT	DOSE	ROUTE	COMMENTS
Fluconazole	200 mg/d or 100 mg q 12 hr	PO or IV	If empiric amphotericin preparations are used, hold fluconazole or voriconazole for the duration of amphotericin-based therapy.
Ciprofloxacin	500 mg q 12 hr	PO	Discontinue when broad-spectrum IV antibiotics are started. Note that bioavailability of cipro is reduced if co-administered with agents containing magnesium, aluminum or calcium (e.g., antacids, sucralfate).
Acyclovir	800 mg q 12 hr or 250 mg/m ² q 12 hr	PO or IV	Use only in patients who are seropositive for herpes simplex virus or have a history of HSV infection.

Antimicrobial prophylaxis should be given to all patients during the induction therapy. Treatment with all agents (except for fluconazole and acyclovir) will start at the initiation of induction chemotherapy, if not started previously, and stop when the absolute granulocyte count is >

500/mcl. During each cycle of consolidation it is recommended that the same treatment be resumed on Day 7 and stopped when the absolute granulocyte count is > 500 /mcl. If the absolute granulocyte count does not drop below 500/mcl following chemotherapy, then the antimicrobial prophylaxis should be stopped on Day 21 of each cycle.

b. Management of Infection and Use of Antibiotics

1. Any neutropenic patient (absolute granulocyte count < 500 /mcl) with an oral temperature exceeding 38°C on more than one occasion within a single (24 hour) day or a single temperature greater than 38.5°C should have broad-spectrum intravenous empiric antibiotics started expeditiously at the discretion of the treating physician. Prior to antibiotic administration urine culture, urinalysis and 2 sets of blood cultures should be obtained. Careful physical exam and chest radiograph should also be performed. Oral ciprofloxacin prophylaxis should be stopped when empiric intravenous antibiotics are started.
2. There are many appropriate choices of broad-spectrum empiric antibiotics for use in the febrile neutropenic patient. The regimen should be chosen based on the susceptibility pattern of the predominant pathogens at the treating hospital. Possible regimens to use are listed below.
 - i. Monotherapy with imipenem
 - ii. Combination therapy with an anti-pseudomonal penicillin (piperacillin) and a third generation cephalosporin (ceftazidime or cefoperazone).
 - iii. Combination therapy with an anti-pseudomonal penicillin (piperacillin) and an anti-pseudomonal aminoglycoside (amikacin).
 - iv. Combination therapy with a third generation cephalosporin (ceftazidime or cefoperazone) and an anti-pseudomonal aminoglycoside (amikacin).
3. If the patient is persistently febrile after 72 hours, additional antibiotic and/or antifungal coverage should be considered. If culture data indicate a more favorable antibiotic regimen, then the appropriate antibiotics will be substituted. An infectious disease consultant should be considered for patients with persistent fever at 72 hours while receiving adequate antibiotic coverage. Although vancomycin is not recommended for empiric use, it should be noted that the use of ciprofloxacin may increase the emergence of streptococci and coagulate-negative staphylococci.
4. Patients placed on aminoglycosides should be carefully followed for renal insufficiency and for appropriate serum drug levels. Any patient placed on amphotericin B should be carefully monitored for renal insufficiency, hypokalemia and hypomagnesemia.
5. The patient will be continued on broad-spectrum antibiotics until the absolute granulocyte count is > 500 /mcl and the patient is afebrile.

c. Blood Product Support

1. The hemoglobin should be maintained at a safe level, especially in severely thrombocytopenic patients (e.g., hemoglobin > 8 - 10 grams/dl).
2. The platelet count should be maintained greater than 10,000/mcl in non-bleeding patients. In the presence of fever or hypertension, platelet transfusion to 20,000/mcl is recommended. In the presence of active hemorrhage or suspected gastrointestinal bleeding, platelet transfusion to a minimum count of 50,000/mcl is recommended. Maintenance of platelet count of 30,000-50,000/mcl, particularly at or near the time of diagnosis and initiation of therapy, is recommended, particularly in the setting of active DIC.
3. Patients who are refractory to random donor platelets (single donor or pooled) should receive HLA-matched platelet transfusions if possible. An unsatisfactory one-hour platelet count increment is less than 20% of expected rise (expected rise is 5,000 per unit platelets transfused).
4. Cryoprecipitate should be administered to maintain the fibrinogen at a level of 100-150 mg/dl.

d. Mucosal and Nutritional Considerations

1. Mucositis may be severe. Although prophylactic use of fluconazole and acyclovir is expected to reduce infectious causes, mucosal lesions should be cultured for fungal, viral and bacterial organisms.
2. Malnutrition may be severe and prolonged in elderly patients undergoing intensive chemotherapy. Early institution of hyperalimentation is recommended when oral intake becomes inadequate.

e. Growth Factors

1. Growth factors (e.g., GM-CSF, G-CSF, or erythropoietin) may be used at the discretion of the treating physician in cases of serious or life-threatening infection. It should be pointed out that the benefit of growth factors in this setting is unclear.

7.10 Intake Calendar

ATRA, 6-MP, and methotrexate drug compliance will be recorded by patients on the Intake Calendar (see Appendix [18.3](#)). Institutional CRAs will review and ascertain patient adherence with protocol treatment. Do not submit the Intake Calendar to the Data Operations Center.

7.11 Criteria for Removal from Protocol Treatment

- a. Patients whose pretreatment RT-PCR assays are found to be PML-RAR α -negative will be removed from protocol treatment and receive no further treatment under this protocol (see Section [7.3d](#)).
- b. Delay of more than 5 days prior to initiation of gemtuzumab ozogamicin during induction.
- c. Patients who fail to achieve A1 marrow, B1 blood, and C1 extramedullary disease status (see Section [10.1](#)) within 90 days of initiation of induction therapy will not be eligible for consolidation therapy and will receive no further treatment under this protocol.

- d. Unacceptable toxicity as defined in Section [8.0](#).
- e. Patients who do not maintain CR or relapse before or while receiving consolidation or maintenance therapy.
- f. Patients who become pregnant.
- g. Successful completion of all stages of therapy.
- h. The patient may withdraw from the study at any time for any reason.

7.12 Discontinuation of Treatment

All reasons for discontinuation of treatment must be documented on the Off Treatment Notice.

7.13 Follow-Up Period

All patients will be followed until death or a maximum of 3 years from time of initial registration.

8.0 TOXICITIES TO BE MONITORED AND DOSAGE MODIFICATIONS

8.1 NCI Common Terminology Criteria for Adverse Events (CTCAE)

Two different versions of the NCI Common Terminology Criteria for Adverse Events (CTCAE) will be used on this study.

a. Serious Adverse Event (SAE) reporting

The CTCAE (NCI Common Terminology Criteria for Adverse Events) Version 4.0 will be utilized for SAE reporting only. The CTCAE Version 4.0 is identified and located at the CTEP website at http://ctep.cancer.gov/protocolDevelopment/electronic_applications/ctc.htm. All appropriate treatment areas should have access to a copy of the CTCAE Version 4.0.

b. Routine toxicity reporting

This study will utilize the CTCAE Version 3.0 for routine toxicity reporting. A copy of the CTCAE Version 3.0 can be downloaded from the CTEP home page (<http://ctep.cancer.gov>). All appropriate treatment areas should have access to a copy of the CTCAE Version 3.0.

8.2 Toxicities to be Monitored

The toxicities of the agents included in this regimen are well established, and are outlined above in Section [3.0](#). Dose modifications of study medications will be made based upon attribution of toxicity to drug therapy rather than disease.

8.3 Induction Therapy

a. Dose Modifications for ATRA During Induction

- Commonly observed toxicities with ATRA include hepatotoxicity (increased AST and ALT), neurologic changes (headache or pseudotumor cerebri), mucocutaneous changes (dry skin, peeling of palms and soles) and others including cheilitis, epistaxis, fatigue, musculoskeletal pain, and conjunctivitis. If a patient experiences a Grade 3 toxicity, ATRA will be held until the toxicity has resolved to \leq Grade 1. At that time, restart ATRA at 75% dose. Recurrent episodes of \geq Grade 3 toxicity will result in discontinuation of ATRA until the toxicity resolves to \leq Grade 1; ATRA will then be resumed with an additional 25% dose reduction. Patients requiring dose reductions that would reduce the dose to less than 25% of the starting dose should be removed from ATRA (continue other therapy) for the remainder of the cycle. ATRA may be used again in subsequent cycles if toxicity has resolved to \leq Grade 1.
- The ATRA syndrome should be treated as outlined in Section [7.3b](#).
- If ATRA related Grade \geq 3 toxicity (excluding ATRA syndrome) does not resolve to \leq Grade 1 within 14 days of occurrence, ATRA will be permanently discontinued.

CLOSED EFFECTIVE 06/01/2013

b. Dose Modification for Arsenic Trioxide During Induction

Missed doses due to holidays or dose modifications will not be made up. Modification of the arsenic dose in these cycles should be made as follows:

- Renal Toxicity

Creatinine	Adjust Dose:
≥ 1.5 x baseline but < 3.0 mg/dL	Hold treatment until creatinine < 1.5 x baseline, then resume treatment at full dose.
≥ 3.0 mg/dL or oliguric renal failure	Hold treatment until creatinine < 1.5 x baseline, then resume treatment with a 50% dose reduction (0.075 mg/kg/day)*

* If toxicity persists for more than 14 days or recurrent renal toxicity occurs despite a dose reduction, then discontinue arsenic trioxide.

Hepatotoxicity: Give the following dose, based on lab values obtained within 2 days prior to therapy

AST (SGOT)	Bilirubin	Adjust dose:
> 5-fold increase over ULN	2-3 fold increase over upper limit of normal (ULN) > 3-fold increase over ULN	Hold treatment until bilirubin < 2x ULN, then resume at full dose Hold treatment until AST < 3x ULN or bilirubin < 2x ULN, then resume treatment with a 50% dose reduction (0.075 mg/kg/day)*

* If toxicity persists for more than 14 days or recurrent hepatotoxicity occurs despite a dose reduction, then discontinue arsenic trioxide.

Hematologic Acute Hemolysis: In the case of acute hemolysis (CTCAE 3.0 Grade ≥ 3), hold treatment until complete resolution, then resume treatment with a 50% dose reduction (0.075 mg/kg/day). No dose adjustment is necessary for pancytopenia of any grade. If toxicity persists for more than 14 days after holding treatment or recurrent acute hemolysis occurs despite dose reduction, then discontinue arsenic trioxide.

Dermatologic Toxicity: In the case of rash (CTCAE 3.0 Grade ≥ 3), hold treatment until clear clinical evidence of improvement to ≤ Grade 1, then resume treatment with a 50% dose reduction (0.075 mg/kg/day). If toxicity persists for more than 14 days after holding treatment or recurrent dermatologic toxicity occurs despite dose reduction, then discontinue As₂O₃.

Nausea/Vomiting: Nausea/vomiting of any grade should be handled with symptomatic treatment with anti-emetics. If CTCAE 3.0 Grade ≥ 3 vomiting occurs despite adequate trial of anti-emetics, then hold treatment until clinical improvement and then resume treatment at full dose. If treatment-refractory

nausea/vomiting recurs, then hold treatment until improvement is \leq Grade 1 and then resume treatment with a 50% dose reduction (0.075 mg/kg/day). If toxicity persists for more than 14 days after holding treatment or recurrent nausea and vomiting occur despite dose reduction and anti-emetics, then discontinue As_2O_3 .

- **Neurologic Toxicity:** In the case of moderate-severe objective sensory loss or paresthesias; motor weakness; clinically evident hearing loss; locomotor ataxia or dysmetria; agitation, confusion, or hallucination then hold treatment until clear clinical evidence of resolution to \leq Grade 1 and then resume treatment with a 50% dose reduction (0.075 mg/kg/day). If toxicity persists for more than 14 days after holding treatment or recurrent moderate-severe neurologic toxicity occurs despite dose reduction, then discontinue As_2O_3 .
- **Cardiac Toxicity:** Guidelines for the management of prolonged QTc interval are as follows:
 - EKG must be obtained twice weekly during induction therapy and as clinically indicated.
 - Measure the QT interval (from the start of the Q wave to the end of the T wave) and the preceding RR interval. The QTc interval will be calculated as the QT interval (msec) divided by the square root of the RR interval (msec).
 - QTc interval $<$ 500 msec: No specific therapy needed. Continue As_2O_3 . Serum K^+ and Mg^{++} should be monitored and repeated only if low.
 - QTc interval 500-600 msec: Hold As_2O_3 temporarily and replete serum K^+ and Mg^{++} with IV and/or oral K^+ and Mg^{++} to minimum target levels of 4.0 and 2.0 mg/dL, respectively. Resume As_2O_3 on same day if target levels are achieved and re-check prior to next dose.
 - QTc interval $>$ 600 msec: Hold As_2O_3 . Aggressive IV K^+ and Mg^{++} repletion (for adults $MgSO_4$ can be given as 2 g IV, followed by up to 12 g in 6 hours). If the QTc interval falls below 600 msec, the patient can be sent home with additional oral supplements and should return the following day for re-checking prior to further As_2O_3 treatment. If the QTc interval does not fall below 600 msec with this level of repletion, the patient should undergo EKG monitoring by telemetry, preferably in the hospital, along with continued IV K^+ and Mg^{++} .
 - **Other Arsenic Trioxide-Related Toxicity:** If Grade \geq 3, then hold treatment until clear clinical evidence of resolution to \leq Grade 1 and then resume treatment with a 50% dose reduction (0.075 mg/kg/day). If toxicity persists for more than 14 days after holding treatment or recurrent toxicity occurs despite dose reduction, then discontinue As_2O_3 .

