	Infections and Infestations - Other (opportunistic infection associated with >=Grade 2 lymphopenia)	
INJURY, POISONING AND PROCEDURAL COMPLICATIONS		
	Bruising	Bruising
INVESTIGATIONS		
	Alanine aminotransferase increased	Alanine aminotransferase increased
	Aspartate aminotransferase increased	Aspartate aminotransferase increased
	Blood bilirubin increased	Blood bilirubin increased
	Creatinine increased	Creatinine increased
	Electrocardiogram QT corrected interval prolonged	Electrocardiogram QT corrected interval prolonged
	GGT increased	GGT increased
	Lipase increased	Lipase increased
Neutrophil count decreased		Neutrophil count decreased
Platelet count decreased		Platelet count decreased
	Serum amylase increased	Serum amylase increased
	Weight gain	Weight gain
	Weight loss	Weight loss
	White blood cell decreased	White blood cell decreased
METABOLISM AND NUTRITION DISORDERS		
	Acidosis	Acidosis
	Anorexia	Anorexia
	Hyperglycemia	Hyperglycemia
	Hyperkalemia	
	Hypokalemia	Hypokalemia
	Hypomagnesemia	Hypomagnesemia

MUSCULOSKELETAL AND CONNECTIVE TISSUE DISORDERS		
	Arthralgia	Arthralgia
	Bone pain	Bone pain
	Generalized muscle weakness	Generalized muscle weakness
	Musculoskeletal and connective tissue disorder - Other (muscle atrophy)	Musculoskeletal and connective tissue disorder - Other (muscle atrophy)
	Myalgia	Myalgia
NERVOUS SYSTEM DISORDERS		
	Dizziness	Dizziness
Headache		Headache
	Paresthesia	
	Peripheral motor neuropathy	Peripheral motor neuropathy
	Peripheral sensory neuropathy	Peripheral sensory neuropathy
PSYCHIATRIC DISORDERS		
	Anxiety	
	Insomnia	Insomnia
RENAL AND URINARY DISORDERS		
	Acute kidney injury	Acute kidney injury
	Proteinuria	Proteinuria
RESPIRATORY, THORACIC AND MEDIASTINAL DISORDERS		
	Allergic rhinitis	Allergic rhinitis
	Bronchospasm	Bronchospasm
	Cough	Cough
Dyspnea		Dyspnea
	Epistaxis	
	Laryngeal mucositis	Laryngeal mucositis
	Pharyngeal mucositis	Pharyngeal mucositis
	Pleural effusion	Pleural effusion
	Retinoic acid syndrome	Retinoic acid syndrome
	Sore throat	
	Tracheal mucositis	Tracheal mucositis
SKIN AND SUBCUTANEOUS TISSUE DISORDERS		
	Alopecia	Alopecia
	Dry skin	Dry skin
	Hyperhidrosis	Hyperhidrosis
Pruritus		Pruritus
	Purpura	Purpura
Rash maculo-papular		Rash maculo-papular

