7.1 Good Medical Practice

This clinical trial can fulfill its objectives only if patients appropriate for the trial are enrolled. All relevant medical and other considerations should be taken into account when deciding whether this protocol is appropriate for a particular patient. To maximize patient safety, patients should be treated on this protocol only at centers having ready access to blood product support and adequate staff to care for the severely neutropenic patient with multiple-therapy induced toxicities. Physicians should consider the risks and benefits of any therapy, and, therefore, only enroll patients for whom the agents administered are appropriate. Although they will not be considered as formal eligibility criteria, as part of this decision-making process, physicians should recognize that the following problems may increase the risk to the patient entering this protocol. These are guidelines, not strict eligibility criteria. See Section 5.0 for strict eligibility criteria. These guidelines apply to all registration steps (Initial Registration, Consolidation Therapy Registration, and Maintenance Therapy Registration).

- a. Patient should not have other serious illnesses that would limit survival to < 2 years.
- b. Patient should not have psychiatric conditions that would prevent compliance with treatment or informed consent.
- c. Patient should not have uncontrolled or severe cardiovascular or pulmonary disease. This would include history of a recent acute myocardial infarction, congestive heart failure, or active angina.
- d. Abnormalities in measured parameters of hepatic and renal function must be considered as potentially serious obstacles for safe tolerance of the therapy prescribed in this protocol. The degree to which such perturbations are attributable to comorbid disease or are leukemia-related should be considered in the decision to enroll a patient on this protocol.
- e. Patients who become pregnant after registration must be removed from protocol therapy.

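### Section 8.3b, renal table: arsenic is held for oliguric renal failure, but the release depends on creatinine alone, so the same row can say both hold and resume

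*Combined protocol and SAP*

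**What the plan says.** Section 8.3b of the protocol gives two renal rows for arsenic trioxide in induction.

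- **Row 1.** The trigger is creatinine at or above "1.5 x baseline but < 3.0 mg/dL". The action is "Hold treatment until creatinine < 1.5 x baseline, then resume treatment at full dose".
- **Row 2.** The trigger is creatinine at or above "3.0 mg/dL or oliguric renal failure". The action is "Hold treatment until creatinine < 1.5 x baseline, then resume treatment with a 50% dose reduction (0.075 mg/kg/day".

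A footnote to row 2 adds: "If toxicity persists for more than 14 days or recurrent renal toxicity occurs despite a dose reduction, then discontinue arsenic trioxide".

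Section 8.4d refers back to 8.3b, so the same table governs arsenic in Consolidation Cycles 1 and 2. The study calendar (Section 9.0) schedules creatinine twice weekly in induction and weekly in consolidation. It lists no urine-output check.

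**The concern.** Row 2 has two alternative triggers but only one release, and that release is the same creatinine line used in row 1, where creatinine is the only trigger. The line suits the creatinine trigger. It does not address the other one: nothing in row 2 asks whether the oliguric renal failure has ended before arsenic restarts.

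What is at stake is dosing safety. The arsenic adverse event list in Section 3.2b includes "Acute kidney injury" among the possible events. A site following the table could find the restart condition satisfied while the reason for the hold is still present.

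**Working it through.** No design figure is involved. The check is whether a patient can meet the row 2 trigger and the row 2 release at the same time.

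**Inputs.** From 8.3b: trigger is C ≥ 3.0 mg/dL or oliguric renal failure; release is C < 1.5 × B; restart dose is 0.075 mg/kg/day. C is current creatinine and B is baseline. The documents give no baseline values, so I assume B from 0.8 to 1.2 mg/dL.

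**Release line, 1.5 × B.**

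| Assumed B (mg/dL) | Release line (mg/dL) |
|---|---|
| 0.8 | 1.5 × 0.8 = 1.2 |
| 1.0 | 1.5 × 1.0 = 1.5 |
| 1.2 | 1.5 × 1.2 = 1.8 |

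**Creatinine trigger.** At each of these baselines the line lies below 3.0, so a patient with C ≥ 3.0 cannot meet the release until creatinine falls. This half of the row works.

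**Oliguric renal failure trigger.** Take a patient in oliguric renal failure, by level of creatinine:

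1. C ≥ 3.0. Row 2 applies on creatinine anyway. The hold binds, but it ends when creatinine falls below the line, whether or not the renal failure has resolved.
2. 1.5 × B ≤ C < 3.0. Row 1 would already hold treatment; the renal failure trigger moves the patient to row 2 and so halves the restart dose. The release again looks only at creatinine.
3. C < 1.5 × B. Only the renal failure trigger applies, and the release is already met. Example: B = 1.0, C = 1.4, and 1.4 < 1.5. The required hold time is zero.

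In case 3 the hold never binds. In cases 1 and 2 it can end while its trigger persists.

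**Comparison with other rules in 8.3b.**

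| Toxicity | Hold ends when |
|---|---|
| Acute hemolysis | the hemolysis has fully resolved |
| Rash | the rash has improved to Grade 1 or less |
| Neurologic | the neurologic toxicity has resolved to Grade 1 or less |
| Other, Grade 3 or higher | that toxicity has resolved to Grade 1 or less |
| Renal row 2, oliguric renal failure | creatinine is below the line; the renal failure is not mentioned |

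Each of the first four rules ends on its own trigger. The hepatic row is worded more loosely and I do not rely on it.

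**Ceiling on exposure.** Suppose the row is read as allowing a restart, creatinine never reaches the line, and the footnote counts unresolved renal failure as persisting toxicity from its onset. Dosing at 5 days a week for 14 days is 10 doses. At 0.075 mg/kg that is 0.75 mg/kg, against 10 × 0.15 = 1.5 mg/kg at full dose. This is a limit under those assumptions, not an expected exposure.

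**The case against.** The strongest reply is that the row does not clearly permit dosing. A reader might infer from the release line that the protocol authorizes arsenic during ongoing renal failure. The documents do not support that. A patient still in oliguric renal failure on the planned restart day still meets the row 2 trigger, and the action for that trigger begins with a hold. The footnote speaks of toxicity and of recurrent renal toxicity, not of creatinine alone, which fits a view of the renal event as continuing until it resolves. This stands: the fault is a row that gives two instructions, and I put it no higher.

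Nor should a reader infer that low urine output alone triggers the row. The trigger is oliguric renal failure, in a column headed by creatinine, and the author may well have taken creatinine as the recovery marker for a condition expected to raise it. The documents do not define the term or show how often it occurs with creatinine below the line. That narrows the case without closing the gap.

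Scheduled monitoring also helps. In induction, physical examination, toxicity notation and creatinine are all twice weekly; in Consolidation Cycles 1 and 2 creatinine is weekly and the examination monthly. Once creatinine reaches 1.5 times baseline, a hold applies under one row or the other. These checks shorten the exposure but add no restart condition tied to the renal failure.

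Other provisions do not supply that condition:

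- The footnote says when to stop arsenic for good, not when it may restart.
- Section 8.2 says "Dose modifications of study medications will be made based upon attribution of toxicity to drug therapy rather than disease", which concerns attribution.
- Section 7.1d says "Abnormalities in measured parameters of hepatic and renal function must be considered as potentially serious obstacles for safe tolerance", but it is guidance for deciding on registration, not a dosing rule.
- The rule for other arsenic toxicity covers toxicities without their own entry, and renal toxicity has one.
- The Study Chair contact in Section 8.7 is for questions; a site that sees the condition met may have none.

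**Conclusion.** The point holds as a minor drafting fault with a safety bearing, at moderate confidence. Row 2 can tell a site both to hold arsenic and to resume it at half dose for the same patient, because one of its two triggers has no matching release. That much follows from the text; the creatinine examples rest on assumed baselines of 0.8 to 1.2 mg/dL.

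The number of patients affected cannot be computed from the documents and is probably small. The upper limit of 20% attached to acute kidney injury in Section 3.2b might be taken as a frequency for this situation. It is a category ceiling for all acute kidney injury and says nothing about renal failure with creatinine still below the line. No endpoint, sample size or decision rule in Section 11 changes. Because the protocol pages are stamped closed effective 06/01/2013, the practical value is mainly in reuse of the table.

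**What to change.** In the second renal row of Section 8.3b, add to the release, directly after the creatinine condition: *and oliguric renal failure (if present) has resolved*. The restart at 0.075 mg/kg/day and the footnote stay as they are. Section 8.4d carries the change into Consolidation Cycles 1 and 2 without further editing. The acute hemolysis rule already uses a resolution standard without a numerical definition, so none is essential here.

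The cost is one phrase and a longer hold in a few patients. No data collection or sample size is added. This is a cheap improvement.
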